
 
• To evaluate the ability of dupilumab in reducing the proportion of patients who require treatment with oral corticosteroids (OCS)
 
• To evaluate safety outcome measures
 
• To evaluate immunogenicity of dupilumab
 
	
 
• Time-to-event and proportion of patients receiving OCS for CSU during the planned treatment period
 
• Percentages of participants experiencing treatment-emergent adverse events (TEAEs) or serious adverse events (SAEs)
 
• Incidence of treatment-emergent anti-drug antibodies (ADA) against dupilumab over time
 

Tertiary/exploratory	

 
• To demonstrate exploratory outcome measures in the urticaria composite score and or its components
 
• To demonstrate exploratory health-related quality-of-life and health status measures
 
• To demonstrate reduction in use of rescue medication
 
	
 
• Time to UAS7 MID response (9.5 to 10.5 points) by Week 12 and Week 24
 
• Change from baseline in the number of itch-free days and/or hive-free days at Week 12 and Week 24
 
• Change in UAS7 in well-controlled patients (UAS <math>\leq</math>6) from Weeks 24 to 36
 
• Change from baseline in EQ-5D-5L (or EQ-5D-Y 5L for <math>\geq</math>6 to <16 years old) at Week 12 and Week 24
 
• Change from baseline in CU-QoL at Week 12 and Week 24
 
• Missed school/work days from baseline at Week 12 and Week 24
 
• Use of antihistamine rescue medication
 
• Total OCS rescue dose prescribed (in mg) during the treatment period
 
• Total OCS rescue intake in days during the treatment period
 

Pharmacokinetic	

 
• To evaluate PK and pharmacodynamic (PD) outcome measures
 
	
 
• Functional dupilumab concentrations in serum and PK profile
 
• Pharmacodynamic response for selected biomarkers (total IgE)
 

a Key secondary endpoint for Study A and B

b Key secondary endpoint for Study C: UAS7 at Week 24 (except EU and EU reference countries, where ISS7 at Week 24 is key secondary endpoint)

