#### Type of participant and disease characteristics

Participants who have a diagnosis of CSU refractory to H1-AH at the time of randomization, as defined by all of the following:

I 02. Diagnosis of CSU  $>6$  months prior to screening visit (Visit 1).

I 03. The presence of itch and hives for  $>6$  consecutive weeks at any time prior to screening visit (Visit 1) despite the use of H1-AH during this time period.

I 04. Participants using a study defined H1-AH for CSU treatment (see [Section 6.1.2](#) for the list of antihistamines allowed for the study). Note: Participants should remain on their prescreening non-sedating H1-AH dose. Only up to 4-fold the recommended dose is allowed. If participants are on dose higher than 4-fold the recommended dose at screening, the Investigator can adjust the participant dose to the stipulated range at the screening visit (Visit 1). The H1-AH dose should be stable for at least 3 consecutive days prior to the screening visit (Visit 1).

I 05. During the 7 days before randomization:

- UAS7  $\geq 16$
- ISS7  $\geq 8$

Note: To be eligible for the study, participants must have no missing electronic diary (e-diary) (UAS7 and ISS7) in the 7 days before randomization.

I 06. Deleted in Amended protocol 02.

I 07. Study A and C (omalizumab naïve): Participants who are omalizumab naïve.  
Study B (omalizumab intolerant or incomplete responders): Omalizumab incomplete responders are defined as participants treated with at least 300 mg (q4w) omalizumab for at least 3 months (minimum of 3 injections) and who have had an inadequate response resulting in omalizumab discontinuation, as confirmed by Investigator assessment.  
Note: Information about intolerance or incomplete response to omalizumab should be well documented in the patient's medical records.

I 08. Participants must be willing and able to complete a daily symptom e-diary for the duration of the study.

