#### **Prior/concomitant therapy**

- E 15. Exposure to another systemic or topical investigative drug (monoclonal antibodies as well as small molecules) within a certain time period prior to the screening visit (Visit 1), defined as follows: an interval of <6 months or <5 PK half-lives for investigative monoclonal antibodies, whichever is longer, and an interval of <30 days or <5 PK half-lives, whichever is longer, for investigative small molecules.
- E 16. Having used any of the following treatments within 4 weeks before the screening visit (Visit 1).
  - Immunosuppressive/immunomodulating drugs (eg, systemic corticosteroids [oral or parenteral - intravenous, intramuscular, SC]), cyclosporine, mycophenolate-mofetil, interferon gamma, Janus kinase inhibitors, azathioprine, methotrexate, hydroxychloroquine, sulfasalazine, dapsone, colchicine, etc).
  - Antifibrinolytic tranexamic acid and epsilon-aminocaproic acid.
  - Leukotriene receptor antagonists (LTRAs) and H2 receptor antagonists. Note: patients taking stable LTRAs and /or H2 receptor antagonists for diseases other than CSU (eg, asthma or gastroesophageal reflux disease, respectively) will be permitted to continue their use.
  - Phototherapy, including tanning beds.

E 17. Treatment with biologics as follows:

- Any cell-depleting agents including but not limited to rituximab: within 6 months before the screening visit (Visit 1).
- Omalizumab within 4 months before the screening visit (Visit 1).
- Other monoclonal antibodies (which are biological response modifiers): within 5 half-lives (if known) or 16 weeks before the screening visit (Visit 1), whichever is longer.

E 18. Treatment with a live (attenuated) vaccine ([Section 10.10](#)) within 4 weeks before the screening visit (Visit 1).

NOTE: For participants who have vaccination with live, attenuated vaccines planned during the course of the study (based on national vaccination schedule/local guidelines), it will be determined, after consultation with a physician, whether the administration of vaccine can be postponed until after the EOS, or preponed to before the start of the study, without compromising the health of the participant:

- Patient for whom administration of live (attenuated) vaccine can be safely postponed would be eligible to enroll into the study.
- Patients who have their vaccination preponed can enroll in the study only after a gap of 4 weeks following administration of the vaccine.

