#### **6.5.1 Rescue medicine**

All participants on 1- to 3-fold the approved non-sedating H1-AH dose (maintenance dose used at screening) will be allowed to take additional doses of their H1-AH medications as rescue therapy as long as they do not exceed 4-fold the recommended dose during the screening, treatment, and follow-up periods. If symptoms are still uncontrolled after increase of H1-AH to the maximum allowed dose, participants can take a short course of OCS as rescue therapy during the treatment and follow-up periods. The participants on stable dose of 4-fold the approved H1-AH dose will be allowed to take a short course of OCS as rescue therapy during the treatment and follow-up periods. In order to ensure consistency, when possible, it is recommended to use OCS for 5 to 7 days with a starting dose of oral prednisone 40 mg (or clinically comparable OCS) followed by taper per the Investigator's judgment.

For rescue medication in participants in Japan, please see Appendix 11 ([Section 10.11](#)).

The initial maintenance antihistamine dose should remain stable throughout the study, and participants should continue their maintenance dose once rescue treatment is no longer required.

The use of permitted rescue medications should be delayed, if possible, for at least 8 weeks following the initiation of the investigational treatment. The date and time of rescue medication administration as well as the name and dosage regimen of the rescue medication must be recorded.

For other information related to H1-AH and OCS including safety precautions please refer to the National Product labeling.

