Secondary Change from baseline in UAS7 at Week 12 and Week 24 (except EU and EU reference countries) Change from baseline in HSS7 at Week 12 and Week 24 Change from baseline in ISS7 at Week 12 and Week 24 (in EU and EU reference countries) Change from baseline in AAS7 at Week 12 and Week 24 Change from baseline in UCT at Week 12 and Week 24 Change from baseline in DLQI /CDLQI at Week 12 and Week 24 PGIC at Week 12 and Week 24 Change from baseline in PGIS at Week 12 and Week 24 Change from baseline in ISS at all time points	These endpoints will be analyzed using the same approach as for the primary endpoint of change from baseline in ISS7 at Week 24.  Detailed analyses will be described in the SAP finalized before database lock.
Secondary Proportion of ISS7 MID responders at Week 12 and Week 24 Proportion of patients with UAS7 $\leq 6$ at Week 12 and Week 24 Proportion of patients with UAS7 = 0 at Week 12 and Week 24	These responder endpoints will be analyzed using the Cochran-Mantel-Haenszel test adjusted by baseline disease severity, presence of angioedema at baseline, and region. The baseline disease severity will be defined according to UAS7 $<28$ or $\geq 28$ . Comparisons of the response rates between dupilumab dose and placebo will be derived.

Endpoint	Statistical analysis methods
Proportion of well-controlled patients (UCT $\geq 12$ ) at Week 12 and Week 24	Participants who receive selected prohibited medications and/or rescue medications will be considered as non-responders for time points after the medication usage. For other participants, all available data including those collected during the off-treatment period will be used to determine the responder/non-responder status. Missing data will be considered as non-responders.
Secondary	
Time to ISS7 MID response	These time-to-event endpoints will be analyzed using the Cox proportional hazards model, including treatment, the corresponding baseline value, presence of angioedema at baseline, and region as covariates. The estimates of the hazard ratio between dupilumab dose and placebo will be derived.
Proportion and time to event of patients receiving OCS for CSU during the planned treatment period	
Exploratory	Will be described in the SAP finalized before database lock.

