For time to participants receiving first OCS for CSU during the planned treatment period, participants who receive selected prohibited medications and/or rescue medications other than OCS for CSU, data prior to start of the medication will be used, but after medication start, the participant will be censored at time of start of medication. Participants who don't receive OCS during the treatment period will be censored at Day 169 or their status date collected on the completion of study/follow-up eCRF form, whichever is earlier. This endpoint will be analyzed using a Cox proportional hazards model, including intervention, presence of angioedema at baseline, and region as covariates.

In addition, secondary endpoints included in the multiplicity procedure ([Section 4.6](#)) will be analyzed in the subgroup of adults and adolescent participants.

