For time to participants receiving first OCS for CSU during the planned treatment period, participants who receive selected prohibited medications and/or rescue medications other than OCS for CSU, data prior to start of the medication will be used, but after medication start, the participant will be censored at time of start of medication. Participants who don't receive OCS during the treatment period will be censored at Day 169 or their status date collected on the completion of study/follow-up eCRF form, whichever is earlier. This endpoint will be analyzed using a Cox proportional hazards model, including intervention, presence of angioedema at baseline, and region as covariates.

Categorical summaries by visit will be provided for PGIC and PGIS.

In addition, secondary endpoints included in the multiplicity procedure ([Section 4.6](#)) will be analyzed in the subgroup of adults and adolescent participants.

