- Time since first diagnosis of CSU (years) to be derived as
(Year of randomization – Year of first diagnosis of CSU) + (month of randomization-month of first diagnosis of CSU)/12
- Presence of angioedema at baseline
 - Number of episodes in past 6 months
 - Time since last episode (months)
- Baseline ISS7 score (quantitative and qualitative variable: <13, \geq 13)
- Baseline UAS7 score (quantitative and qualitative variable: <28, \geq 28)
- Baseline weekly hives severity score (HSS7)
- Baseline angioedema activity score over 7 days (AAS7) for participants with angioedema
- Baseline urticaria control test (UCT)
- Baseline Dermatology Life Quality Index (DLQI)/Children's Dermatology Life Quality Index (CDLQI)
- Baseline Patient Global Impression of Severity (PGIS)
- Frequency of alcohol drinking in the past 12 months (never, occasional, at least monthly, at least weekly, at least daily) and number of drinks on a typical day (1 or 2, >2)
- Baseline IgE (quantitative and qualitative variable: <100 vs \geq 100)
- Baseline H1-AH dose (1-fold, 2-3-fold, 4-fold)

Prior or concomitant medications

All medications taken within 1 month before screening and until the end of the study, including all prior medications taken for CSU are to be reported in the case report form pages.

All medications will be coded using the World Health Organization-Drug Dictionary (WHO-DD) using the version currently in effect at Sanofi at the time of database lock.

- Prior medications are those the participant used prior to first investigational medicinal product (IMP) injection. Prior medications can be discontinued before first administration or can be ongoing during treatment phase.
- Concomitant medications are any interventions received by the participant concomitantly to the IMP, from first administration of IMP to last IMP intake + 98 days.
- Post-treatment medications are those the participant took in the period running from the end of the concomitant medications period up to the end of the study.
- A given medication can be classified as a prior medication and/or as a concomitant medication and/or as post-treatment medication. If it cannot be determined whether a given medication was taken prior or concomitantly or post, it will be considered as prior, concomitant, and post-treatment medication.

The prior and concomitant medications will be summarized for the randomized population.

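### The Cox model for time to first oral corticosteroid (OCS) use has no baseline itch or hive severity term: the protocol's covariate is undefined for this endpoint, and the Study C SAP drops it without a substitute.

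*Protocol*

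**What the plan says.** The protocol's secondary endpoint for the OCS objective is "Time-to-event and proportion of patients receiving OCS for CSU during the planned treatment period". Table 7 in Section 9.4.1 groups it with time to ISS7 response and gives both a "Cox proportional hazards model, including treatment, the corresponding baseline value, presence of angioedema at baseline, and region as covariates". The synopsis repeats that model for time-to-event endpoints in general.

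Section 4.4.2 of the Study C SAP separates the OCS endpoint: "This endpoint will be analyzed using a Cox proportional hazards model, including intervention, presence of angioedema at baseline, and region as covariates". The Study A SAP (4.4.1) and the Study B SAP (4.4.2) give the same three terms. None of the three explains why the baseline term has gone. The version history of the Study C SAP reports no major change from the protocol.

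Elsewhere in the Study C SAP, severity is adjusted for:
- Continuous endpoints use the baseline value of the score.
- Responder endpoints use baseline UAS7 below 28 against 28 or more.
- Time to ISS7 response uses its own baseline value.

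Inclusion criterion I 05 requires that "participants must have no missing electronic diary (e-diary) (UAS7 and ISS7) in the 7 days before randomization".

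**The concern.** A covariate written into the protocol cannot be fitted for one of the two endpoints it is assigned to. OCS is a treatment event, not a score. Exclusion criterion E 16 removes systemic corticosteroid use in the four weeks before screening, so there is no earlier OCS measure to stand in. The SAP's response is to delete the term, not to replace it.

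Baseline disease severity probably predicts who needs OCS. Leaving a prognostic factor out of a Cox model gives up some power, and any chance imbalance in it goes uncorrected. It also means that the reported hazard ratio is not conditional on severity, unlike the one for time to ISS7 response. At stake is the precision of the hazard ratio for reduced OCS use, an endpoint likely to have few events.

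**Working it through.** **1. What the plan powers.** No power, event count, OCS rate or hazard ratio is given for OCS. The Study C calculation concerns the primary endpoint and reproduces: 4.23 / 7.5 = 0.564; 75 × 0.90 = 67.5 evaluable per arm; a two-sided t-test at 0.05 then has 90.2% power, against the stated 90%. It says nothing about OCS.

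**2. Events to expect.** With placebo risk p over 24 weeks, the dupilumab risk is 1 − (1 − p)^HR, and total events are D = 75 × (sum of the two risks). Approximate power is Φ(√D × |ln HR| / 2 − 1.96). Assuming HR 0.5:

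| Placebo OCS risk (assumed) | Events | Power |
|---|---|---|
| 10% | 11.3 | 21% |
| 20% | 22.9 | 38% |
| 30% | 34.8 | 53% |

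For 80% power, D = 4 × (1.96 + 0.84)² / (ln 0.5)², about 66 events. The shortage of events limits this endpoint far more than any covariate does.

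**3. Effect of a severity covariate alone.** Simulated Cox models with 150 participants, true conditional HR 0.5, 3,000 replicates per setting, and neither angioedema nor region in the model:

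| Severity HR per SD (assumed) | HR without severity, at 10 / 20 / 30% risk | Power without → with, 10% | 20% | 30% |
|---|---|---|---|---|
| 1.0 | 0.494 / 0.502 / 0.499 | 13.7 → 13.4% | 33.9 → 34.1% | 50.4 → 50.0% |
| 1.5 | 0.504 / 0.504 / 0.509 | 13.9 → 14.0% | 32.0 → 33.4% | 48.5 → 49.2% |
| 2.0 | 0.503 / 0.515 / 0.525 | 13.1 → 13.9% | 32.5 → 34.7% | 45.8 → 51.3% |
| 3.0 | 0.524 / 0.540 / 0.548 | 11.9 → 13.1% | 28.9 → 35.7% | 39.1 → 52.5% |

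Monte Carlo error on each power figure is about 0.9 points. Up to HR 2.0 per SD, the gain is about 0 to 6 points and the HR shift at most about 0.025. Only the extreme 3.0 gives about 13 points. Angioedema and region would absorb part of any severity effect, so this set-up tends to overstate the gain.

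**4. Closer to the planned model.** With angioedema and four regions in both models, 75 per arm, 10% early censoring, true HR 0.45 and about 16 to 33 events, adding baseline UAS7 changes power by about 0 to 4 points over weak to strong prognostic effects. It costs nothing when UAS7 is not prognostic. Rejection under no effect stays near 5%.

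**5. A second candidate covariate.** Section 6.5.1 states that "The participants on stable dose of 4-fold the approved H1-AH dose will be allowed to take a short course of OCS", while participants on lower doses first increase their antihistamine. Adding an indicator for background H1-antihistamine at the maximum allowed dose brings about 0 to 3 points more under assumed effects.

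**The case against.** The strongest reply is that little depends on this. Time to OCS is a supportive secondary endpoint, absent from the Study C hierarchy in SAP Section 4.6 and without stated power, so no confirmatory claim is affected. That stands and sets the severity.

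Four stronger readings are tempting, and the documents do not support them.

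- **That the model has no baseline disease measure.** Presence of angioedema at baseline stays in it. The Study C SAP lists angioedema among the baseline disease characteristics, and it stratifies the randomisation of adults. What is missing is an itch or hive score.
- **That the planned hazard ratio is biased.** The shift towards 1 is non-collapsibility. The less-adjusted hazard ratio is a different estimand, and the randomised test is valid.
- **That this is the only comparative test of OCS use.** Footnote a to Table 2 of the Study C SAP sends other secondary endpoints to the method for their type. For proportions that is a CMH test adjusted for angioedema, region and baseline UAS7 category. Table 7 of the protocol sets the OCS proportion beside the Cox text, so the point is arguable, but there is a basis for a severity-adjusted comparison.
- **That background antihistamine dose must be in the model.** Its link to OCS timing is inferred from the rescue rules in 6.5.1. The documents give no supporting data, and no planned main efficacy model adjusts for it.

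Sparse events are also a fair caution. Region has four levels in Study C, so the planned model already has five parameters (intervention 1, angioedema 1, region 3). With about 17 events (75 × (0.15 + 0.0705) = 16.5, at 15% placebo risk and HR 0.45), one more makes six, or 17 / 6 ≈ 2.8 events per parameter. The simulated rejection rate near 5% is reassuring, but the cost is not nil.

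**Conclusion.** The gap is real and small. Table 7 prescribes a covariate that does not exist for time to OCS. The Study C SAP removes it without replacement or comment, leaving this model without the severity adjustment used for the responder endpoints and for time to ISS7 response. The planned analysis is valid but slightly inefficient. Adding baseline UAS7 is worth about 0 to 4 points of power at weak to strong prognostic effects, and it makes the hazard ratio conditional on severity. That size rests wholly on assumed OCS rates, hazard ratios and prognostic effects. If UAS7 does not predict OCS use, there is no gain. This is a cheap improvement of low severity.

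**What to change.** In Study C SAP Section 4.4.2 and protocol Table 7, before unblinding, specify the time-to-OCS Cox model as intervention, continuous baseline UAS7, presence of angioedema at baseline and region. Keep the baseline-value wording for time to ISS7 response only, and align the matching sentence in the synopsis. Background H1-antihistamine at the maximum allowed dose (yes/no) may be added as a covariate in an optional sensitivity analysis.

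The cost is one line of text, no new data and one extra parameter in a model with few events. If the sponsor prefers the three-term model, Table 7 should say that no baseline value applies to OCS, so that protocol and SAP agree.

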#### 9.4.2 Safety analyses

All safety analyses will be performed on the safety population. The summary of safety results will be presented by treatment group. The baseline value is defined generally as the last available value before randomization.

**Table 8 - Safety analyses**

Endpoint	Statistical Analysis Methods
AE, SAE, AE leading to death, AE leading to permanent treatment discontinuation	
Adverse event incidence tables will present by system organ class (SOC) (sorted by internationally agreed order), high-level group term (HLGT), high level term (HLT) and preferred term (PT) sorted in alphabetical order for each treatment group, the number (n) and percentage (%) of participants experiencing an AE. Multiple occurrences of the same event in the same participant will be counted only once in the tables within a treatment phase. The denominator for computation of percentages is the safety population within each treatment group.
 
Proportion of participants with at least 1 treatment-emergent adverse event (TEAE), treatment-emergent SAE, TEAE leading to death, and TEAE leading to permanent treatment discontinuation will be tabulated by treatment group. In addition, TEAEs will be described according to maximum intensity and relation to the study intervention. Serious AEs and AEs leading to study discontinuation that occur outside the treatment-emergent period will be summarized separately.

Endpoint	Statistical Analysis Methods
AESI and other AE groupings	
Incidence of each type of AESI and other AE groupings will be tabulated by treatment group. For each type of AESI, the following analysis will be generated.
 
 
• A summary of the number (%) of participants with 
 
- Any TEAE
 
- Any SAE (regardless of treatment-emergent status)
 
- Any treatment-emergent SAE
 
- Any AE leading to death
 
- Any TEAE leading permanent treatment discontinuation
 
- Any TEAE related to study intervention reported by the Investigator
 
- Any TEAE by maximum intensity, corrective treatment, and final outcome
 
 
 
• Kaplan-Meier (K-M) estimates of probability of having at least one TEAE at specific time points, and K-M curve to depict the course of event onset over time.
 
 
The method to identify AESIs and other AE groupings will be specified in the SAP.

Death	
The following deaths summaries will be generated:
 
 
• Number (%) of participants who died by study period (TEAE, on-study) summarized on the safety population by treatment received.
 
• Death in nonrandomized participants or randomized and not treated participants.
 
• TEAE leading to death (death as an outcome on the AE eCRF page as reported by the Investigator) by primary SOC, HLGT, HLT, and PT showing number (%) of participants sorted by internationally agreed order of SOC and alphabetic order of HLGT, HLT, and PT.
 

Laboratory parameters	
Results and change from baseline for the parameters will be summarized by treatment group for baseline and each post baseline time point, endpoint, minimum and maximum value. Summary statistics will include number of participants, mean, standard deviation, median, Q1, Q3, minimum, and maximum.
 
The following definitions will be applied to laboratory parameters.
 
 
• The potentially clinically significant abnormality (PCSA) values are defined as abnormal values considered medically important by the Sponsor according to predefined criteria/thresholds based on literature review and defined by the Sponsor for clinical laboratory tests.
 
• PCSA criteria will determine which participants had at least 1 PCSA during the on-treatment period, taking into account all evaluations performed during the on-treatment period, including unscheduled or repeated evaluations. The number of all such participants will be the numerator for the on-treatment PCSA percentage.
 
 
The proportion of participants who had at least one incidence of PCSA at any time during the treatment emergent period will be summarized by treatment group. Shift tables showing changes with respect to the baseline status will be provided.

